1.3 Summary of Clinical Experience

1.3.1 Clinical Safety

As of 09 May 2023 (data cut-off date), Hengrui Pharmaceuticals Co., Ltd has initiated 3 clinical studies (two Phase I and one Phase II) of AIO-001 (SHR-1905). Two clinical studies (SHR-1905-101 and SHR-1905-201) were performed in China, and the other one (SHR-1905-I-101-AUS) was conducted in Australia. A total of 147 subjects received AIO-001, including 100 healthy subjects were exposed to AIO-001 (n=80) or placebo (n=20) at a single dose of 50 - 600 mg, 12 patients with mild asthma received a single subcutaneous dose of 200 mg AIO-001 (n=8) or placebo (n=4), 24 patients with moderate or severe asthma received a single subcutaneous dose of 100/600 mg AIO-001 (n=16) or placebo (n=8), and 11 patients with severe asthma received multiple subcutaneous doses of CCI AIO-001 or placebo.¹

Among 100 healthy subjects exposed to AIO-001/placebo, 63 subjects (63.0%) experienced TEAEs, which occurred in $\geq 5\%$ of the subjects included blood thyroid stimulating hormone increased, blood uric acid increased and blood bilirubin increased (7.0% each), bilirubin conjugated increased, aspartate aminotransferase increased, headache and alanine

aminotransferase increased (6.0% each), and haemoglobin decreased and blood creatine phosphokinase increased (5.0% each).¹

Among 47 patients with asthma who were exposed to AIO-001/placebo, the incidence of TEAEs was 31.9% (15/47), including alanine aminotransferase increased, blood creatine phosphokinase increased, blood uric acid increased and triiodothyronine free increased (2 subjects each), and the others were seen in single subjects.¹

All TEAEs above were mild or moderate in severity, which can be controlled with or without medical intervention. No subjects experienced serious adverse events (SAEs) or fatal TEAEs. No subjects withdrew from studies due to TEAEs.¹

1.3.2 Pharmacokinetics and Immunogenicity in Humans

Following a single SC injection of AIO-001 from 50 mg to 600 mg in Australian healthy subjects (SHR-1905-I-101-AUS) (N=40), the serum concentrations of AIO-001 increased along with the increased dose level. CCI [REDACTED]

To explore the dose proportionality of AIO-001 in tested dose range (50 mg to 600 mg) in healthy subjects, C_{max} , $AUC_{0\text{-last}}$, and $AUC_{0\text{-inf}}$ were further examined against dose using power model. The slopes of CCI [REDACTED] indicating that the exposure of AIO-001rs to increase in a slightly greater-than-dose-proportional manner with increased dose from 50 mg to 600 mg. The slopes of CCI [REDACTED] CCI [REDACTED], indicating that the exposure of AIO-001 appears to increase in a slightly greater-than-dose-proportional manner with increased dose from 50 mg to 600 mg.¹

In all the Australian healthy subjects (N=50) in this study, treatment-induced ADA positive subjects were reported in both placebo group CCI [REDACTED] and AIO-001 treatment group CCI [REDACTED]. Treatment-induced ADA positive subjects with AIO-001 were: CCI [REDACTED] CCI [REDACTED]. There was CCI [REDACTED] subject in the placebo group who had a pre-existing ADA sample at baseline. The observed earliest time point of treatment-induced ADA after AIO-001 Treatment started from CCI [REDACTED] in the 200 mg and 600 mg group, and CCI [REDACTED] in the 400 mg group. There was no obvious effect observed in corresponding PK concentrations in all the ADA positive subjects.¹

1.4 Study Rationale

[figure not shown]
Existing safety data from China and Australia Phase 1 single ascending dose studies of AIO-001 are from subjects who received SC injections with a 100 mg/ml formulation requiring multiple 1 ml injections to achieve doses up to 600 mg. The study in China also included subjects with asthma.

In a proposed phase 2 trial, Aiolos Bio will be utilizing a new formulation and subjects will receive two SC injections of 1.1 ml at AIO-001 concentration of 182 mg/ml to achieve a 400 mg dose. The primary purpose of the present study is to compare the safety, tolerability, and PK parameters of 400 mg of AIO-001 as the new formulation (Formulation B) with a 400 mg dose of AIO-001

administered as the original formulation (Formulation A) in healthy volunteers. Pharmacokinetic parameters and other primary and secondary endpoints will be described and compared quantitatively.

1.4.1 Rationale for the Dose

[figure not shown]
CCI

1.4.2 Rationale for the Study Population

A healthy volunteer population has been selected for the study because healthy subjects with no concomitant diseases and using no concomitant medications represent a homogenous population allowing for proper evaluation of the PK, safety, and tolerability of a drug without confounding factors.

CCI

The effects of AIO-001 on fertility, pregnancy and lactation in human have not been investigated so far. Since there have been no studies with pregnant women, it is uncertain whether there is human fetal risk associated with the use of AIO-001. Therefore, only male and non-pregnant, non-lactating female subjects will be included in the study. Non-sterile males and females of childbearing potential will be included if they use appropriate methods of contraception.

1.5 Benefit/Risk Assessment

The inclusion and exclusion criteria have been chosen to select subjects who are known to be free from any significant illness, history of autoimmune diseases, and from any condition that could impact their safety or interfere with meeting the study objectives. The proposed safety screening and monitoring assessments are deemed to be sufficient to monitor potential risks of AIO-001 administration. There is no anticipated therapeutic benefit for the healthy subjects in this study.

So far, as mentioned before, a total of 147 subjects received AIO-001/placebo, including 100 healthy subjects were exposed to AIO-001 or placebo (n=20) at a single dose of 50 – 600 mg, 12 patients with mild asthma received a single subcutaneous dose of 200 mg AIO-001 (n=8) AIO-001 or placebo (n=4), 24 patients with moderate or severe asthma received a single subcutaneous dose of 100/600 mg AIO-001 (n=16) or placebo (n=8), and 11 patients with severe asthma received multiple subcutaneous doses of [REDACTED] mg AIO-001 or placebo. [REDACTED]

All the safety data obtained so far was with AIO-001 using Formulation A. Although this is the first time the new Formulation (Formulation B) will be tested in humans, this study will evaluate Formulation B, and a similar safety profile is expected. All excipients are generally recognised as safe. The information obtained in this study may help in the treatment of future patients with severe, uncontrolled asthma.

2. Objectives

Primary objective:

- To compare the safety and tolerability of 400 mg of AIO-001 as the new formulation (Formulation B) with a 400 mg dose of AIO-001 administered as the original formulation (Formulation A) in healthy volunteers.

Secondary objectives:

- To evaluate the PK of a single SC AIO-001 dose of Formulation A in healthy volunteers.
- To evaluate the PK of a single SC AIO-001 dose of Formulation B in healthy volunteers.
- To evaluate the immunogenicity of AIO-001 in healthy volunteers.

3. Endpoints

Primary endpoints:

- Adverse events (AEs), vital signs measurements (blood pressure, heart rate, respiratory rate, and tympanic temperature), 12-lead electrocardiogram (ECG) recordings, physical examinations, and clinical laboratory test results, including hematology, biochemistry, and urinalysis.

Secondary endpoints:

- PK endpoints may include but are not limited to AIO-001 concentrations, $AUC_{0-\text{last}}$, $AUC_{0-\text{inf}}$, C_{\max} , T_{\max} , $T_{1/2}$.
- Incidence of anti-drug antibody (ADA) to AIO-001.

4. Study Design

This is an open-label single dose, parallel group, 24-week phase 1 study in 16 healthy subjects.

The study is designed to evaluate and compare the safety, tolerability, pharmacokinetics, and immunogenicity of subcutaneously (SC) administered AIO-001 at a total dose of 400 mg using two different formulations (original Formulation A and new Formulation B) in 16 healthy volunteers (8 receiving each formulation).

The study will include a screening visit from Day -28 to Day -2 (Visit 1). Eligible subjects will be admitted to the clinical site on Day -1 and will be confined until completion of the assessments on Day 3 (Visit 2). Subjects will return to the clinical site for outpatient visits for study assessments and laboratory tests as described in the [Table 1. Schedule of Assessments](#).

A staggered dosing schedule will be used for dosing of each cohort and will include 2 sentinel subjects (1 for each formulation) dosed initially, and the remaining 14 subjects dosed at least 24 hours later.

The total duration of study participation for each subject from screening through the EOS is anticipated to be approximately 28 weeks.

5. Study Population

5.1 Number of Subjects

It is planned to enroll up to 16 healthy subjects for participation in this study. The proposed number of subjects is in line with the sample sizes commonly used in clinical studies of this nature and is considered sufficient to achieve the study objectives.

5.2 Inclusion Criteria

Subjects must meet all of the following criteria to be included in the study:

1. Able to understand the study procedures and provide signed informed consent to participate in the study.
2. Male or female.
3. Non-smokers. Light smokers (no more than 5 cigarettes daily [approximately 50 to 60 mg of nicotine per day], or products with equivalent amount of nicotine within 3 months prior to screening) may be permitted.
4. ≥ 18 and ≤ 55 years of age.
5. BMI > 18.5 and $< 32.0 \text{ kg/m}^2$ and body weight $\geq 45.0 \text{ kg}$.
6. Healthy subjects as defined by:
 - a. the absence of clinically significant illness and surgery within 4 weeks prior to dosing.
 - b. the absence of clinically significant history of neurological, endocrine, cardiovascular, respiratory, hematological, immunological, psychiatric, gastrointestinal, renal, hepatic, and metabolic disease.
7. Female subjects of non-childbearing potential must be:
 - a. post-menopausal (spontaneous amenorrhea for at least 12 months prior to dosing) with confirmation by documented FSH levels $\geq 40 \text{ mIU/mL}$; or
 - b. surgically sterile (bilateral oophorectomy, bilateral salpingectomy, or hysterectomy) at least 3 months prior to dosing.
8. Sexually active female subjects of childbearing potential who are sexually active with the opposite sex and non-sterile male subjects must be willing to use an acceptable contraceptive method throughout the study as detailed in section 7.1.

5.3 Exclusion Criteria

Subjects to whom any of the following applies will be excluded from the study:

1. Any clinically significant abnormal finding at physical examination at screening.

2. Clinically significant abnormal laboratory test results or positive serology test results for HBsAg, HCV antibody, or HIV antigen and antibody, or QuantiFERON®-TB test at screening.
3. Positive pregnancy test or lactating female subject.
4. Positive urine drug screen or alcohol breath test.
5. History of anaphylaxis, or severe allergy.
6. Previous exposure to thymic stromal lymphopoietin antibody.
7. Known allergic reactions to thymic stromal lymphopoietin antibody drugs and their excipients, or other biologic products or to any excipient in the formulation.
8. Estimated Glomerular Filtration Rate (eGFR, using CKD-EPI Creatinine Equation) < 90 ml/min/1.73m² during screening or baseline visit.
9. Clinically significant ECG abnormalities (e.g., For male QTcF > 450msec, for female QTcF > 470msec) or vital signs abnormalities (systolic blood pressure lower than 90 or over 140 mmHg, diastolic blood pressure lower than 40 or over 90 mmHg, or heart rate less than 40 or over 100 bpm) at screening.
10. History of drug abuse within 1 year prior to screening.
11. History of alcohol abuse within 1 year prior to screening or regular use of alcohol within 6 months prior to screening that exceeds 10 units for women or 15 units for men of alcohol per week (1 unit = 375 mL of beer 3.5%, or 100 mL of wine 13.5%, or 30 mL of distilled alcohol 40%).
12. Use of medications within the timeframes specified in section [7.2](#).
13. Previous participation in a clinical trial of AIO-001.
14. Dosed in a clinical research study involving the administration of an investigational or marketed drug or device within 30 days prior to dosing, administration of a biological product in the context of a clinical research study within 90 days or 5 half-lives (whichever is longer) prior to dosing, concomitant participation in an investigational study involving no drug or device administration.
15. Donation of plasma within 7 days prior to dosing or donation or loss of 500 mL or more of whole blood within 4 weeks prior to dosing.
16. Any reason which, in the opinion of the Investigator, would prevent the subject from participating in the study.
17. Intolerance to venipuncture.
18. Any scars, tattoos, etc., at the injection site.
19. More than 5 cigarettes daily (or products with equivalent amount of nicotine) for 3 months prior to screening and unable to abstain from smoking during the trial.

5.4 Subject Withdrawal and Replacement

Subjects will be advised that they are free to withdraw from the study at any time. Over the course of the study, the Sponsor and the Investigator or designee may withdraw any subject from the study for one of the reasons described below; subject withdrawal will be done in accordance with the local guidance at the clinical site:

- Safety reason;
- Non-compliance with protocol requirements;
- Significant protocol deviation;
- Positive pregnancy test, drug screen or alcohol breath test.

Subjects who withdraw prior to dosing may be replaced automatically. In the event that the number of drop-outs exceeds initial expectations, subjects who withdraw or are withdrawn from the study after dosing, for reasons other than safety and tolerability, may be replaced after consultation between the Investigator and the Sponsor. In such case, the total number of subjects dosed will remain within a maximum of 10 subjects for Groups A and B.

Subjects who withdraw or are withdrawn on Day-1 to Day 3 will be asked to remain at the clinic until the Investigator or designee agrees that the subject is fine and can be discharged. A PK blood sample may be collected at the time of withdrawal if deemed required by the Investigator. End of study EOS/ET procedures will be performed at the time of withdrawal from the study or as soon as possible thereafter.

6. Study Treatments

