Abbreviations: ADA=, anti-drug antibody; AE = adverse event; BMI = body mass index; d = Day; ECG = electrocardiogram; EOS = end of study; ET = early termination; FSH = follicle-stimulating hormone; h = hour; HBsAg = hepatitis B surface antigen; HCV = hepatitis C virus; HIV = human immunodeficiency virus; PK = pharmacokinetic; TB= tuberculosis;

1. Subjects will remain in the investigational study center from check-in on Day -1 until after the 48 hours PK samples and all other required assessments are completed on Day 3 (Visit 2).
2. Beginning at Day 8 (Visit 6), for operational feasibility surrounding Public Holidays, an additional +1day visit window may be granted with sponsor approval.
3. In case of ET, EOS procedures will be performed as soon as possible.
4. A complete physical examination will be performed at screening. A brief physical examination will be performed on Day -1 (Visit 2), at Day 85 (Visit 14), and at Day 169 (Visit 17) (EOS/ET).
5. Weight and BMI only.
6. Includes blood pressure, heart rate, respiration rate, and tympanic temperature.
7. Serology tests include HBsAg, HCV antibody, and HIV antigen and antibody.
8. COVID-19 screening will be performed according to clinical site's procedure.
9. Standard biochemistry, coagulation, lipid profile, thyroid function, and urinalysis tests will be performed.

Note: IgE is not an eligibility determining assessment and therefore results are not needed prior to eligibility confirmation.

10. FSH levels will be measured at screening to confirm the post-menopausal status.
11. A serum pregnancy test will be performed at screening and at EOS/ET, and a urine pregnancy test will be performed on Day -1 (Visit 2).
12. Refer to [Table 2](#) for more details.
13. Group A: 400 mg of 100 mg/ml AIO-001 as Formulation A, given as 4 X 1.0 ml subcutaneous injections administered within approximately 5 minutes.
- Group B: 400 mg of 182 mg/ml AIO-001 as Formulation B, given as 2 X 1.1 ml subcutaneous injections administered within approximately 5 minutes.

Note:

- When the timing of multiple procedures coincides, the following priority order should be adhered to, whenever possible: vital signs, ECGs, blood samples for PK/ADA analysis, clinical laboratory samples, physical examination.

-Unscheduled visits are allowed, as needed.

1. Introduction

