6.4 Study Drug Administration

The study drug (AIO-001 injection Formulation A or B) will be injected subcutaneously on Day 1. For safety reasons, subjects will be required to remain seated or semi-reclined during dosing.

- Formulation A: Subjects from Group A will receive 400 mg of 100 mg/ml AIO-001, given as 4 X 1.0 ml subcutaneous injections administered within approximately 5 minutes. The four injection sites are two injection sites on each upper arm separated from each other by at least 5 cm.
- Formulation B: Subjects from Group B will receive 400 mg of 182 mg/ml AIO-001 given as 2 X 1.1 ml subcutaneous injections administered within approximately 5 minutes. The 2 injection sites are one on each upper arm.

IP should not be administered on skin disfigurements or lesions such as scars, tattoos, wounds, bruises, redness and hardening. Please refer to Pharmacy Manual for more details.

The start time of the first injection will be called “0” hour.

7. Study Restrictions

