8.3.2 Recording of Adverse Events

AEs will be recorded and evaluated for their seriousness, severity, and relationship to the study drug. AEs will be collected and documented from the time of signing the ICF and throughout the study. AEs will be followed-up until complete resolution, or until the Investigator or designee judges safe to discontinue follow-up. The severity of AEs and relationship to the study drug will be classified according to the sections below.

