8.3.6 Reporting of Adverse Events

8.3.6.1 Serious Adverse Event Reporting to the Sponsor

Any SAE will be reported to the Sponsor (or representative) within 24 hours of learning of the event. The notification must be directed to:

Aiolos Bio Clinical Safety

Email: [contact]

Information on SAEs will be recorded on the SAE Report Form. Blank copies are included in the study Investigator's file. It is not acceptable for the Investigator to send photocopies of the patient's medical records to the Sponsor company or its representative in lieu of completion of the appropriate AE eCRF page or SAE Report Form. However, there may be instances when copies of medical records for certain cases are requested by the Sponsor or its representative. In this instance, all subject identifiers will be blinded on the copies of the medical records before submission to the Sponsor or its representative.

The completed SAE Form and SAE cover sheet should be sent via e-mail immediately upon completion to Aiolos Bio Clinical Safety. If the Investigator does not have all information regarding an SAE, he/she will not wait to receive additional information before completing and sending the form.

Additional relevant information or clinical follow-up should be sent via e-mail to Aiolos Bio Clinical Safety as soon as it becomes available. The Investigator should follow the subject with the event until resolution or stabilization of the condition. Follow-up reports (as many as required) should be completed and faxed/e-mailed following the same procedure above.

A final report is required once the condition is resolved or stabilized and no more information about the event is expected. The final report should be completed and e-mailed following the same procedure above.

The Investigator must keep a copy of all documentation related to the event in the clinical site files.

If the Investigator learns of any SAE, including death, at any other time after a subject completes the study, and he/she considers the event reasonably related to the study drug, the Investigator will promptly notify the Sponsor/Medical Monitor.

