3.5 Subject Withdrawal and Replacement

Subjects will be advised that they are free to withdraw from the study at any time. Over the course of the study, the Sponsor and the Investigator or designee may withdraw any subject from the study for one of the reasons described below; subject withdrawal will be done in accordance with the local guidance at the clinical site:

- Safety reason;
- Non-compliance with protocol requirements;
- Significant protocol deviation;
- Positive pregnancy test, drug screen or alcohol breath test.

Subjects who withdraw prior to dosing may be replaced automatically. In the event that the number of dropouts exceeds initial expectations, subjects who withdraw or are withdrawn from the study after dosing, for reasons other than safety and tolerability, may be replaced after consultation between the Investigator and the Sponsor. In such case, the total number of subjects dosed will remain within a maximum of 10 subjects for groups A and B.

4. Endpoints

- Primary Endpoints:
 - Adverse events (AEs), vital sign measurements (blood pressure, heart rate, respiratory rate, and tympanic temperature), 12-lead electrocardiogram (ECG) recordings, physical examinations, and clinical laboratory test results, including hematology, biochemistry, and urinalysis.
- Secondary Endpoints:
 - PK endpoints may include but are not limited to AIO-001 concentrations, AUC_{0-last}, AUC_{0-inf}, C_{max}, T_{max}, T_{1/2}.

This document is confidential.

- Incidence of anti-drug antibody (ADA) to AIO-001.

Analysis Populations

All subjects' inclusion status into each analysis population will be determined after database lock. Subjects will be analyzed according to the treatment received.

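### After the single Day 1 dose, subjects can be withdrawn from the study for safety, non-compliance or deviation, and nothing secures their remaining scheduled assessments

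*Protocol*

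**What the plan says.** - **Dosing.** Protocol 6.4 says the study drug "will be injected subcutaneously on Day 1". There is no later dose. Scheduled follow-up runs to Day 169.
- **Withdrawal.** Protocol 5.4: "the Sponsor and the Investigator or designee may withdraw any subject from the study for one of the reasons described below". The reasons are safety, non-compliance, a significant deviation, and a positive pregnancy, drug or alcohol test. SAP 3.5 repeats the rule ("may withdraw any subject from the study for one of the reasons described below") with the same reasons.
- **What follows withdrawal.** Protocol 5.4: "End of study EOS/ET procedures will be performed at the time of withdrawal from the study or as soon as possible thereafter". Table 1 note 3 says the same. SAP 3.5 sets no procedures at withdrawal. Protocol 5.4 adds an in-clinic stay for withdrawals from Day -1 to Day 3 and a PK sample at the Investigator's discretion.
- **Replacement.** Under both documents, dosed subjects who withdraw or are withdrawn "for reasons other than safety and tolerability, may be replaced after consultation between the Investigator and the Sponsor", within a maximum of 10.
- **Event-driven follow-up.** Protocol 8.3.2: "AEs will be followed-up until complete resolution, or until the Investigator or designee judges safe to discontinue follow-up". Protocol 8.3.6.1 follows SAEs to resolution or stabilization, and 8.3.7 follows pregnancies. The Table 1 notes add: "Unscheduled visits are allowed, as needed".

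**The concern.** In a multiple-dose trial, withdrawing a subject for safety or non-compliance at least stops further exposure. Here, once Day 1 is over, there is no exposure left to stop. Removing the subject from the study costs scheduled observation and protects nobody from further drug.

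Three uses of the data are affected:

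- **Safety**, the primary endpoint. A safety reason is the first listed ground, so late vital signs, ECGs and laboratory results can be absent because something happened to the subject. Replacement excludes safety and tolerability withdrawals, so it does not help there. For the other grounds it can add a full profile but leaves the short one in place.
- **Immunogenicity.** One post-dose ADA measurement admits a subject to the population (SAP 4.4). A subject with no induced or boosted positive sample counts as ADA-negative (SAP 8), so brief follow-up can read as a negative result.
- **PK.** AUC0-last enters the B/A comparison in SAP 7.4. A profile cut short by withdrawal gives a smaller AUC0-last for reasons unrelated to the formulation.

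**Working it through.** **1. Does any text secure the remaining visits?** The documents give no figure to reproduce on this point, so the relevant provisions are set side by side.

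| Provision | What it secures | What it leaves open |
|---|---|---|
| Protocol 5.4; Table 1 note 3 | One EOS/ET assessment | Scheduled visits after it |
| Protocol 5.4, Day -1 to Day 3 | Observation until fit for discharge | Everything after discharge |
| Protocol 5.4, PK sample | Nothing; it is optional | Later PK |
| Protocol 8.3.2 | Follow-up of AEs already recorded | Scheduled vital signs, ECG, laboratory, PK, ADA |
| Protocol 8.3.6.1 | SAE follow-up; later related SAEs "at any other time after a subject completes the study" | A withdrawn subject has not completed the study |
| Table 1 notes, unscheduled visits | Permission only | Any requirement; SAP 5.2 also keeps unscheduled data out of summary tables unless used as baseline |
| SAP 5.4 | Inclusion of captured data after non-consent withdrawals | Whether anything further is captured |

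No entry asks a withdrawn subject to keep attending.

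**2. How much follow-up is unsecured?** Inputs are Protocol Tables 1 and 2. Outpatient visits fall on Days 4, 5, 6, 8, 11, 15, 22, 29, 43, 57, 71, 85, 113, 141 and 169, which is 15, each with a PK sample. Post-dose ADA days are 8, 15, 22, 29, 57, 85, 141 and 169, which is 8.

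| Withdrawal at | Visits left | Net of ET visit | Days left of 168 | ADA samples held, incl. ET |
|---|---|---|---|---|
| Day 15 | 9 | 8 | 169 − 15 = 154 (92%) | 2 + 1 = 3 |
| Day 29 | 7 | 6 | 169 − 29 = 140 (83%) | 4 + 1 = 5 |
| Day 85 | 3 | 2 | 169 − 85 = 84 (50%) | 6 + 1 = 7 |

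The last column assumes that the ET visit, which is required, adds one ADA sample to those already taken.

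**3. ADA.** One subject in 8 is 12.5 percentage points, but only if that subject would later have turned positive. Earlier ADA rates are redacted. At an assumed chance of 5–30%, the expected shift given one such withdrawal is 12.5 × 0.05 = 0.6 to 12.5 × 0.30 = 3.8 points.

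**4. AUC0-last.** Half-life and Tmax are not shown in the documents, so I assumed 20–80 days and 5–14 days. The model has one compartment with first-order absorption:

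- k = ln 2 / half-life, and ka solves ln(ka/k)/(ka − k) = Tmax.
- AUC(0–T) is proportional to (1 − e^(−kT))/k − (1 − e^(−ka·T))/ka.
- r = AUC(0–T)/AUC(0–168 days), with T = 14, 28 or 84 days for Days 15, 29 and 85.
- If the eight profiles are otherwise alike, the group geometric mean is multiplied by r^(1/8).

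Example with half-life 80 days and Tmax 14 days: k = 0.00866, ka = 0.248, AUC to 14 days = 9.28, AUC to 168 days = 84.5. So r = 0.110, and 0.110^(1/8) = 0.76, a fall of 24%.

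| Withdrawal at | r | Fall, n = 8 | Fall, n = 9 (one replacement) |
|---|---|---|---|
| Day 15 | 0.110–0.348 | 12–24% | 11–22% |
| Day 29 | 0.247–0.600 | 6–16% | 6–14% |
| Day 85 | 0.659–0.945 | 1–5% | 1–5% |

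These falls occur only if the subject is kept after the case-by-case review in SAP 4.3.

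**5. How likely is a safety withdrawal?** Protocol 1.3.1 reports no withdrawals for TEAEs among 147 subjects, placebo included. The one-sided 95% upper bound is 1 − 0.05^(1/147) = 2.0%, or 16 × 0.020 = 0.3 subjects here. On the 80 + 8 + 16 = 104 with stated AIO-001 exposure it is 1 − 0.05^(1/104) = 2.8%, or about 0.5 of 16. The documents give no rate for non-compliance or deviation withdrawals.

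**The case against.** The strongest reply is that little would be lost in practice.

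- **The triggering event is followed.** Protocol 8.3.2 follows it to resolution, and the required ET visit repeats the EOS assessments, including PK and ADA. This stands. What remains open is scheduled surveillance after that visit.
- **Withdrawal is discretionary and rare.** The rule permits withdrawal without requiring it, and earlier experience shows none for TEAEs. Drug and alcohol screens are scheduled only before dosing, and the only scheduled post-dose pregnancy test is at EOS/ET, so positive-test grounds should seldom arise. This also stands, with the limit that all earlier safety data are from Formulation A.
- **PK safeguards exist.** SAP 4.3 names incomplete data as a ground for review, and SAP 7.3 flags AUC0-inf when residual area exceeds 20%. Under the model above, residual area at Day 15 would be 65–92%. This stands in part. The flag does not cover AUC0-last, and it needs an estimable Kel. With Tmax at 14 days, a Day 15 withdrawal leaves no points after the peak, so Kel and residual area could not be computed.
- **Safety analysis is descriptive**, and the disposition summary shows who left and why. True, but describing the loss does not recover the data.
- **Local site guidance**, which Protocol 5.4 invokes and which is not supplied, may require more. It may, but it is not a protocol requirement.

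A reader might infer that visits must stop at withdrawal. The documents do not say so: unscheduled visits are allowed, and SAP 5.4 sets no time limit on captured data after a non-consent withdrawal. Nor does SAP 3.5 limit follow-up to EOS/ET procedures, since it has no such sentence.

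**Conclusion.** The point holds as a gap in what the plan secures. After the only dose, a subject can be removed from the study for a safety reason, non-compliance or a significant deviation. Beyond one EOS/ET assessment, the early in-clinic stay, an optional PK sample and event-driven follow-up, the remaining scheduled assessments are not secured. That is 8, 6 or 2 outpatient visits net of the ET visit for withdrawal at Day 15, 29 or 85, with normally 3, 5 or 7 ADA samples held against 8 planned.

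It would be wrong to read the 12–24% fall in AUC0-last as an expected bias. It needs a Day 15 withdrawal, the assumed half-life and Tmax, and retention after the SAP 4.3 review. The ADA effect likewise needs later conversion in that subject. The case is probably uncommon. The point is a cheap, minor improvement, justified because late data lost in a group of 8 cannot be recovered.

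**What to change.** Add to Protocol 5.4:

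> After dosing, subjects who meet a listed reason will be asked to complete the scheduled safety, PK and ADA visits to Day 169 unless they withdraw consent or the Investigator judges the visits unsafe; the reason is recorded as an event or deviation. Pregnancy follows 8.3.7.

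Amend the replacement sentence in Protocol 5.4 and SAP 3.5 so that post-dose replacement is limited to subjects who actually leave follow-up for reasons other than safety and tolerability, within the stated maximum of 10. This avoids replacing someone who is still being followed. The attendance sentence is operational and need not be repeated in the SAP.

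**Cost.** No visit or sample is added to the schedule. The change needs a protocol amendment with IEC approval and possibly a consent update; under Protocol 11.1 a revised form requires each subject's further consent. Data from non-compliant subjects must be flagged and their PK inclusion reviewed under SAP 4.3.

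**Limits.** Voluntary withdrawal is unaffected, and a subject already missing visits may still not attend.
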